4.7.2 Secondary Biomarker Analyses

K-M curves and a log-rank test will be used to evaluate the differences in PFS between bTMB mutation high versus low groups as measured by an NGS-based mutation burden assay in blood at various cutoff points other than the primary cut off points 16 and 10. These cutoff points are defined as range 4 to 24 by twos and quartiles.

Descriptive statistics for PFS curves including median PFS time and 6-, 9-, and 12-month PFS probabilities will be estimated for various bTMB cutoff points. OS will be analyzed in a similar way as PFS. ORR and DCR will also be summarized by various bTMB cutoff points. The Brookmeyer-Crowley methodology will be used to construct the CI for the median. Greenwood's formula will be used to construct the CI for the landmark PFS.

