3.1 Protocol Synopsis

The protocol synopsis (see protocol).

3.2 Objectives and Endpoints:

The objectives and corresponding endpoints for the study are outlined in table below.

Objectives	Corresponding Endpoints
Primary Efficacy Objective:	
To evaluate the clinical efficacy of Atezolizumab	ORR according to RECIST v1.1 as assessed by the investigator
Secondary Efficacy Objective:	
To evaluate the efficacy of Atezolizumab	Investigator-assessed PFS according to RECIST v1.1
	Investigator-assessed disease control rate and duration of response according to RECIST v1.1
	Overall survival
Safety Objective:	
To evaluate the safety and tolerability of atezolizumab	Incidence of adverse events, with severity determined through use of NCI CTCAE v4.0
Primary Biomarker Objectives:	
To evaluate whether "positive" bTMB (defined as bTMB ≥ 16 , and bTMB ≥ 10) is associated with improved PFS with the treatment of atezolizumab	Relationship between PFS and bTMB (≥ 16 vs < 16) and between PFS and bTMB (≥ 10 vs < 10)
Secondary Biomarker Objective:	
To evaluate whether "positive bTMB" defined at various bTMB cutoff points or quantiles can predict for improved PFS with atezolizumab.	Relationship between PFS and various bTMB cutoff points, defined as range 4 to 24 by twos, and quantiles, except the primary cutoff points 16 and 10
To evaluate the correlation between clinical outcomes including but not limited to PFS rate at 6, 9, and 12 months, ORR, disease control rate and various definitions of positive bTMB.	Relationship between efficacy endpoints including PFS rate at 6, 9, and 12 months, disease control rate, ORR and various bTMB cutoff points and quantiles

Exploratory Biomarker Objectives in Blood:	
To evaluate whether higher expression of an immune-related gene signature in blood PBMCs predicts for improved PFS with atezolizumab	Relationship between PFS and expression of an immune gene signature in PBMCs
To assess whether bTMB is altered as a result of treatment with immunotherapy	Relationship between bTMB and treatment with immunotherapy
To assess the status of additional circulating biomarkers related to immunotherapy and NSCLC and outcomes with atezolizumab	Relationship between circulating biomarkers related to immunotherapy and NSCLC and efficacy
Exploratory Biomarker Objectives in Tissue:	

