4. STATISTICAL METHODOLOGIES

4.1 Sample size:

The sample size for this study is based on the primary efficacy objective and primary biomarker objectives. Based on 150 patients, the maximum half width of the 2-sided 95% CI of the estimated ORR will be within 8%. Additionally, based on 150 patients, there will be at least 80% power to detect a statistical improvement in PFS for bTMB high group vs bTMB low subgroup. The power listed in the table below is based on the following assumptions: the test is 2-sided, significance level is 0.10, both biomarker subgroups have at least 25% of the patients (i.e., 37 or more patients in both groups), median PFS is 4 months for the subgroup with a shorter median PFS, the HR of PFS between the subgroup with a shorter PFS versus the other subgroup is 0.6 or lower, the recruitment duration is one year, the follow-up time from last patient in is 18 months, and the dropout rate is 5%.

n =150	Power		
	Biomarker ≥ 25th percentile vs.< 25th percentile	Biomarker ≥ 50th percentile vs. < 50th percentile	Biomarker ≥ 75th percentile vs. < 75th percentile
0.4	100%	100%	100%
0.5	97%	99%	97%
0.6	83%	92%	84%
0.7	58%	69%	58%

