4.7.1 Primary Biomarker Analyses

K-M curves and a log-rank test will be used to evaluate the differences in PFS between bTMB high versus low groups at 16 and 10 two different cutoff points (i.e. bTMB ≥ 16 vs < 16 , and bTMB ≥ 10 vs < 10). The Gatekeeping testing procedures will be used to test PFS differences at these two primary bTMB cut off points. PFS difference at cutoff point 16 will be tested first. If there is statistical significance in PFS difference bTMB ≥ 16 vs < 16 groups, we will claim statistical significant difference in PFS between bTMB ≥ 16 vs < 16 groups, and we will further test PFS difference at cutoff 10. We can only claim PFS difference between bTMB ≥ 10 vs < 10 groups if both tests for cutoff point 16 and cut off point 10 are statistically significant.

The statistical tests for primary analysis as well as for other analyses comparing efficacy differences between bTMB high group vs low group will be two-sided at a significance level of 0.10. The corresponding bTMB group differences will be estimated and two-sided 90% confidence interval will be provided. All other statistical tests used in the study will be two-sided at level of 0.05. Their corresponding point estimators will be estimated and two-sided 95% confidence interval will be provided.

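### SAP 4.7.2 tests 12 further bTMB cutoffs at the full two-sided 0.10 with no adjustment or descriptive label; with no true association, some cutoff is significant in about 40-45% of trials under assumed bTMB distributions, and in about 20-24% in favour of high bTMB

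*SAP*

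**What the plan says.** SAP 4.7.1 tests PFS at bTMB 16 first, and at 10 only if 16 is significant: "The Gatekeeping testing procedures will be used to test PFS differences at these two primary bTMB cut off points". The same section sets the level for everything else of this kind: "other analyses comparing efficacy differences between bTMB high group vs low group will be two-sided at a significance level of 0.10".

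SAP 4.7.2 then states that "K-M curves and a log-rank test will be used to evaluate the differences in PFS between bTMB mutation high versus low groups", "at various cutoff points other than the primary cut off points 16 and 10". The set is given as follows: "These cutoff points are defined as range 4 to 24 by twos and quartiles".

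The objectives table in SAP 3.2 lists the matching endpoint as "Relationship between PFS and various bTMB cutoff points, defined as range 4 to 24 by twos, and quantiles", again excluding 16 and 10. The objective beside it asks whether positive bTMB at these cutoffs predicts better PFS. That table says quantiles, without a number, where 4.7.2 says quartiles.

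Section 4.7.2 contains no multiplicity adjustment, no condition that the test at 16 or 10 has succeeded, no minimum group size, and no statement that the p-values are descriptive. It uses the term descriptive statistics for medians and landmark PFS rates.

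**The concern.** Two cutoffs are ordered so that the error rate for claims about them is held at 0.10. Twelve more, on the same score and the same patients, are each tested at that level with no control. If bTMB has nothing to do with PFS, the chance that some secondary cutoff looks significant is well above 10%. If 16 fails, the report can still show another cutoff as significant at the plan's own stated level.

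At stake is the reading of the secondary biomarker objective. A reader who sees one cutoff at p < 0.10 will take it as support for that cutoff, and the SAP gives no rule for discounting it.

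**Working it through.** **Count.** From 4 to 24 by twos is 11 values. Removing 16 and 10 leaves 9: 4, 6, 8, 12, 14, 18, 20, 22 and 24. Three quartile splits make 9 + 3 = 12. Because the score is an integer, a quartile can coincide with a fixed cutoff. On average about 10 to 11 splits are distinct (7 to 8 if scores are tightly clustered), and the simulation below allows for this.

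**Does the trial model match the plan?** SAP 4.1 gives n = 150, two-sided 0.10, median PFS 4 months in the shorter group, 12 months of accrual, 18 months of follow-up after the last patient, and 5% dropout (taken here as 5% over 30 months). With exponential PFS:

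- hazard in the shorter group: λ = ln 2 / 4 = 0.1733 per month; dropout hazard δ = −ln(0.95)/30 = 0.00171
- event probability with k = λ + δ: (λ/k) × [1 − (e^(−18k) − e^(−30k)) / (12k)]
- power = Φ(|ln HR| × √(d·p(1−p)) − 1.645), where d is expected events and p the share in one group

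For HR 0.6 and a 50/50 split, the event probabilities are 0.972 and 0.901, so d = 75 × 0.972 + 75 × 0.901 ≈ 140.5. Then 0.511 × √(140.5 × 0.25) = 3.03, and Φ(3.03 − 1.645) = 91.7%, against 92% in the SAP. All nine cells for HR 0.5 to 0.7 agree within 2 points:

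| HR | SAP table (25th / 50th / 75th percentile split) | Recomputed |
|---|---|---|
| 0.5 | 97 / 99 / 97% | 96.5 / 99.2 / 97.3% |
| 0.6 | 83 / 92 / 84% | 82.9 / 91.7 / 84.2% |
| 0.7 | 58 / 69 / 58% | 57.5 / 68.6 / 58.3% |

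**Familywise rate.** Twelve independent tests would give 1 − 0.9^12 = 71.8%. These tests cut the same patients on one score and are strongly correlated, so that is only an upper reference. The rate was therefore simulated: PFS unrelated to bTMB (median 4 months), accrual, follow-up and dropout as above, and log-rank tests at all 12 cutoffs at two-sided 0.10. There were 8,000 trials per setting, with n = 150 (SAP 4.1) and n = 120 (evaluable patients in Protocol 6.1). The bTMB distribution is an assumption throughout. LN is lognormal (median, log-SD) and NB is negative binomial (mean, size). Each cell shows n = 150 / n = 120, in percent.

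| Assumed bTMB | Any of 12 significant | Any, high bTMB better | Any, counting only splits with about 25% or more per side | Any, given 16 not significant |
|---|---|---|---|---|
| LN 8, 0.9 (central) | 41.2 / 42.7 | 19.5 / 20.2 | 27.1 / 28.3 | 35.0 / 36.4 |
| LN 10, 0.8 (central) | 45.2 / 45.1 | 22.9 / 23.7 | 29.6 / 30.4 | 39.4 / 39.2 |
| NB 10, 1.5 (central) | 44.8 / 45.4 | 20.8 / 21.1 | 28.1 / 29.1 | 38.9 / 39.4 |
| LN 12, 0.8 (central) | 42.6 / 43.8 | 22.1 / 23.8 | 29.6 / 30.3 | 36.9 / 38.2 |
| LN 14, 1.2 | 39.1 / 39.3 | 19.9 / 20.7 | 33.5 / 33.4 | 32.5 / 32.5 |
| LN 5, 1.3 | 41.7 / 42.5 | 20.0 / 19.5 | 26.4 / 26.8 | 35.1 / 35.9 |
| LN 5, 0.5 | 52.0 / 50.6 | 20.2 / 19.7 | 22.2 / 22.4 | 45.7 / 44.7 |
| LN 10, 0.5 | 55.0 / 56.5 | 29.1 / 30.8 | 25.9 / 26.9 | 50.8 / 52.4 |

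A single test would give 10% in either direction and about 5% in the improved direction.

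**Share of trials where 16 fails and a secondary cutoff succeeds.** The test at 16 is non-significant in about 90% of null trials. Under the central distributions, 0.90 × 35.0% = 31.5% and 0.90 × 39.4% = 35.5%, so roughly 31-35% of all trials. This counts any of the 12. In a lognormal case with about 36, 30 and 25 of 120 patients at or above 14, 16 and 18, the immediate neighbours 14 and 18 alone account for about 7%.

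**What adjustment would need.** Holding the familywise rate at 0.10 needs a per-test level of about 0.013 to 0.016 under the central distributions, and 0.003 to 0.018 over all tried. Bonferroni, 0.10/12 = 0.0083, gives about 6-7.5% centrally but 12-14% under the two narrow distributions (log-SD 0.5), where very small groups make the log-rank approximation poor.

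**The case against.** **These are secondary analyses in a hypothesis-generating study.** They are labelled secondary. However, Protocol 6.7.2 uses the hypothesis-generating description to justify optional interim analyses, and the SAP does not attach it to these tests. Section 4.7.1 gives them a significance level. If they are meant to be descriptive, the SAP should say so.

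**The primary claims are intact.** This stands. A reader might infer that the ungated tests defeat the gatekeeping at 16. The documents do not support that: the rules on what may be claimed are in SAP 4.7.1 and cover only 16 and 10, so a significant result at 14 or 18 permits no claim at either.

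**The grid does not choose a threshold.** This also stands. Protocol section 2 speaks of defining positivity retrospectively, but the SAP fixes 16 and 10 in advance and nowhere says that the secondary grid will select a cutoff.

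**Either-direction counting overstates the problem.** Partly right. The objective concerns improved PFS, for which the rate is about half, 20-24%. That is still four to five times the 5% of one test. Counting only splits with about 25% or more of patients per side, which is the SAP's own power assumption, gives 22-34% in either direction.

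**OS.** Section 4.7.2 says OS is handled like PFS, and a reader might infer 12 more log-rank tests and a combined rate of 63-70%. That is not established: the OS sentence follows the one on medians and landmark rates and may mean only those.

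**Conclusion.** The concern holds in a limited form. Twelve secondary PFS tests each carry two-sided 0.10 with no adjustment, no link to the gatekeeping and no descriptive label. With no association between bTMB and PFS, at least one is significant in about 40-45% of trials under the central distributions (39-57% over all tried), and about 20-24% (up to 31%) in the improved direction. In about 31-35% of trials 16 fails and some secondary cutoff is significant.

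The count and the level come from the SAP. The percentages rest on assumed bTMB distributions, since the documents give none, and should be quoted as ranges. The count of 12 also rests on quartiles in 4.7.2; the unspecified quantiles in 3.2 could change it. The defect is confined to the secondary objective. Error control for the claims at 16 and 10 is unaffected.

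**What to change.** 1. In SAP 4.7.2, report the non-primary cutoffs and quartile splits descriptively, with K-M curves, hazard ratios and 90% confidence intervals and no significance statement. Apply the same to OS if log-rank tests are intended there.
2. In SAP 4.7.1, amend the sentence on the significance level so that, for bTMB comparisons, 0.10 applies only to 16, then 10.
3. Reconcile quantiles in SAP 3.2 with quartiles in 4.7.2.
4. Optionally, add one Cox model of PFS on log2(bTMB + 1), either as a descriptive dose-response estimate or as a third step tested only after 16 and 10 are both significant. It should not be a free-standing test at 0.10: with no association, the chance that it or the test at 16 is falsely significant would then be about 15-17%.

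Descriptive reporting is preferable to an adjusted level because the level needed depends on a bTMB distribution that the plan does not state. The cost is SAP wording, plus one model if the option is taken. Data collection, sample size and the primary analyses do not change. The downside is that no individual secondary cutoff can be called significant.

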4.7.3 Exploratory Biomarker Analyses

Change in blood-based mutational load after immunotherapy will be analyzed.

The relationship between PBMCs and PFS may be analyzed in a similar way similar as bTMB and PFS, in order to explore whether higher expression of an immune-related gene signature in blood PBMCs predict improved PFS with atezolizumab.

Status of additional circulating biomarkers related to immunotherapy in NSCLC at pre-specified timepoints and outcomes with the study drug will also be summarized in a similar way as bTMB.

The relationship between blood-based mutation load and tissue-based mutation load may also be explored.

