Appendix 2 Schedule of Biomarker Samples

Visit	Timepoint	Sample Type	Proposed Biomarkers	Mandatory/Optional
Screening (Day -28 to Day -1)	NA	Plasma	bTMB	Mandatory
Baseline (Day 1 of Cycle 1)	Prior to infusion	Plasma	bTMB	Mandatory
Baseline (Day 1 of Cycle 1)	Prior to infusion	PBMC	Immune gene expression	Mandatory
Day 1 of Cycle 2	Prior to infusion	Plasma	bTMB	Mandatory
Day 1 of Cycle 2	Prior to infusion	PBMC	Immune gene expression	Mandatory
Day 1 of Cycle 3	Prior to infusion	Plasma	bTMB	Optional
Day 1 of Cycle 4	Prior to infusion	Plasma	bTMB	Mandatory
During treatment	At radiographic progression or loss of clinical benefit	Plasma	bTMB	Mandatory
During treatment	At radiographic progression or loss of clinical benefit	PBMC	Immune gene expression	Mandatory
NA	Anytime during study	Tissue	tTMB and somatic alterations	Optional

bTMB = blood tumor mutational burden; NA = not applicable; PBMC = peripheral blood mononuclear cells; tTMB = tissue tumor mutational burden.

Appendix 3

IASLC Lung Cancer Staging Project Proposed for the Eighth Edition of the American Joint Committee on Cancer Non–Small Cell Lung Cancer Staging System¹

T: Primary tumor	
Tx	Primary tumor cannot be assessed or tumor proven by presence of malignant cells in sputum or bronchial washings but not visualized by imaging or bronchoscopy
T0	No evidence of primary tumor
Tis	Carcinoma in situ
T1	Tumor ≤ 3 cm in greatest dimension surrounded by lung or visceral pleura without bronchoscopic evidence of invasion more proximal than the lobar bronchus (i.e., not in the main bronchus) ^a
T1a(mi)	Minimally invasive adenocarcinoma^b
T1a	Tumor ≤ 1 cm in greatest dimension ^b
T1b	Tumor >1 cm but ≤ 2 cm in greatest dimension ^b
T1c	Tumor >2 cm but ≤ 3 cm in greatest dimension ^b
T2	Tumor >3 cm but ≤ 5 cm or tumor with any of the following features ^c : 
 - Involves main bronchus regardless of distance from the carina but without involvement of the carina - Invades visceral pleura - Associated with atelectasis or obstructive pneumonitis that extends to the hilar region, involving part or all of the lung
T2a	Tumor >3 cm but ≤ 4 cm in greatest dimension
T2b	Tumor >4 cm but ≤ 5 cm in greatest dimension

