4.2 Analysis Populations

Efficacy Analysis Population:

The primary Efficacy analyses will include all patients who receive at least one dose of study drug.

Safety Analysis Population:

The safety analyses will be based on all patients who received any dose of atezolizumab during the study treatment period.

Biomarker Analysis Population:

Biomarker analyses will include all patients who receive at least one dose of study drug and have evaluable baseline biomarker assessment.

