4.5.2 Secondary Efficacy Endpoints

Secondary efficacy endpoints include disease control rate (DCR), duration of response (DOR), and PFS, per RECIST v1.1, and OS. Disease control rate (DCR) is defined as the rate of patients with complete or partial response as best response or stable disease maintained for 24 weeks per RECIST v1.1. DOR will be analyzed for the subset of patients who achieved an objective response. DOR is defined as the time from the initial occurrence of documented CR or PR until documented disease progression as determined by the investigator or death, whichever occurs first. Median and range will be presented for a descriptive summary. Responders with no PD or death, DOR will be censored at last post-baseline tumor assessment. Responders with no post-baseline tumor assessment will be censored at the date of first dose plus 1.

PFS is defined as the time from the first dose of study drug to the time of disease progression or death from any cause during the study, whichever occurs first. Patients who have not experienced disease progression or death at the time of analysis will be censored at the time of the last tumor assessment. Patients with no post-baseline tumor assessment will be censored at the date of first dose plus 1.

OS is defined as the time from the first dose of study drug to the time of death from any cause during the study. Patients who are still alive at the time of analysis will be censored at the date of their last study assessment (for active patients) or at the last date known alive (for patients in follow-up). Patients with no post-baseline assessment will be censored at the date time of first dose plus 1.

PFS and OS of patients in this study will be summarized graphically and with descriptive statistics such as median and landmark PFS by using the Kaplan-Meier (K-M) methodology. The Brookmeyer-Crowley methodology will be used to construct the 95% CI for the median PFS and OS (Brookmeyer and Crowley 1982). K-M methods will also be used to estimate landmark PFS and OS at various time points (i.e., 6, 12, 18, and 24 months), along with the corresponding 95% CI, by using Greenwood's formula.

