4.7 Biomarker Analyses

Biomarker analysis will be based on Biomarker analysis population, which is all patients who receive at least one dose of study drug and have evaluable baseline biomarker assessment, as defined in section 4.2.

The blood tumor mutational burden (bTMB) assay is a blood-based, circulating tumor DNA (ctDNA) next generation sequencing (NGS) test that will be used as an aid in the identification of non-small cell lung cancer (NSCLC) patients most likely to respond to atezolizumab, a

programmed death-ligand (PD-L1) blocking antibody. The NGS-based assay counts the total number of somatic mutations (single nucleotide variants (SNVs) excluding driver mutations) over a 1.25 megabase (Mb) region of coding DNA in ctDNA isolated from fresh plasma derived from whole blood. bTMB is reported as a whole integer score.

The bTMB assay has been analytically validated and clinically validated retrospectively (ESMO 2017 Gandara presentation and Fabrizio poster and manuscript in review). The assay detects SNVs down to 0.5% allele frequency across 394 genes from as little as 1% tumor content in a cell free DNA (cfDNA) sample. Tumor content is estimated by determining the maximum somatic allele frequency (MSAF). All samples in the biomarker evaluable population have MSAF $\geq 1\%$. The FDA approved the IDE for the bTMB assay in 2017, and the assay is now being used to prospectively enroll 1L NSCLC patients in the BFAST trial.

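### SAP 4.7.3 extends the baseline bTMB method, with PFS from first dose, to on-treatment and progression samples; without a landmark rule, Kaplan-Meier summaries are overstated and the log-rank can exceed its nominal level

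*SAP*

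**What the plan says.** SAP 4.7.3 has three relevant statements.

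- Additional circulating biomarkers "at pre-specified timepoints and outcomes with the study drug will also be summarized in a similar way as bTMB".
- For the PBMC immune signature, "The relationship between PBMCs and PFS may be analyzed in a similar way similar as bTMB and PFS".
- For bTMB itself, "Change in blood-based mutational load after immunotherapy will be analyzed", with no method, timepoint or rule for missing samples.

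The method referred to is in SAP 4.7.1: "K-M curves and a log-rank test will be used to evaluate the differences in PFS between bTMB high versus low groups". SAP 4.7.2 repeats it at other cutoffs. The clock is set in SAP 4.5.2: "PFS is defined as the time from the first dose of study drug to the time of disease progression or death from any cause". SAP 4.2 fixes the population by the baseline sample: "Biomarker analyses will include all patients who receive at least one dose of study drug and have evaluable baseline biomarker assessment".

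The samples come from Protocol 3.3.4 and Appendix 2: screening, Day 1 of Cycles 1, 2 and 4, an optional Cycle 3 draw, and a mandatory draw "At radiographic progression or loss of clinical benefit". Scans are every 6 weeks, so the first is due before Cycle 4 Day 1. SAP section 3 allows dosing to continue past RECIST progression under stated conditions.

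SAP 4.7.1 tests bTMB high versus low at two-sided 0.10 and all other comparisons at 0.05. SAP 4.7 adds, on tumor content, "All samples in the biomarker evaluable population have MSAF" of at least 1%.

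Neither document gives a landmark analysis, a time-dependent covariate, or a rule for samples taken after progression. The landmark PFS in SAP 4.5.2 and 4.7.2 means PFS probability at fixed months, which is a different thing.

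**The concern.** A baseline marker is known when the PFS clock starts. A Cycle 4 marker is not. A patient sampled event-free at Cycle 4 Day 1 has already had about two months of PFS that could not have ended, and a first-dose clock counts that time as if it were observed under risk. A patient who progressed at the 6-week scan but stayed on drug can also give a Cycle 4 sample. That marker value is then related to an event that came before it, and may be its consequence. The progression sample is an extreme case: unless it was triggered by loss of clinical benefit, it exists because the outcome occurred.

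At stake is how two listed exploratory objectives can be read: additional circulating markers in relation to outcome, and change in bTMB on treatment. A marker that merely reflects progression could look predictive, and medians by on-treatment marker would not be comparable with the all-treated or baseline-bTMB results.

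**Working it through.** **1. The plan's own figure.** SAP 4.1 gives power for the baseline comparison only; it gives nothing for 4.7.3. Inputs: n = 150, two-sided 0.10, median PFS 4 months in the shorter-PFS subgroup, 12 months' accrual, 18 months' further follow-up, 5% dropout (taken as over 30 months). Schoenfeld power = Φ(√(d·p(1−p))·|ln HR| − 1.645). At HR 0.6:

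| Split at percentile | Events d | Power | SAP |
|---|---|---|---|
| 25th | 137.8 | 82.9% | 83% |
| 50th | 140.5 | 91.7% | 92% |
| 75th | 143.2 | 84.2% | 84% |

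The exponential PFS model used below is therefore consistent with the plan's table.

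**2. Guaranteed time.** Cycle 4 Day 1 is 63 days after first dose: 63/30.44 = 2.07 months. Assume exponential PFS with median 4 months.

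- Event before Cycle 4 Day 1: 1 − 2^(−2.07/4) = 30% in continuous time. Counting only events detected at the 6-week scan, 1 − 2^(−1.38/4) = 21%.
- Median from first dose among those event-free at day 63: 2.07 + 4.0 = 6.1 months, against 4.0 for everyone.
- 6-month PFS: 35.4%/0.699 = 50.6%. 12-month PFS: 12.5%/0.699 = 17.9%.

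The 4-month figure belongs to the shorter-PFS subgroup. With an equal split and HR 0.6, the other median is 4/0.6 = 6.7 months, and scan-detected early events fall from 21% to about 17%.

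**3. Log-rank, event-free patients at one timepoint.** In 3,000 simulated trials with a null marker, n = 150 and first-dose clock, about 105 patients were analysed. Rejection was 10.8% at nominal 10% and 5.4% at nominal 5%, with median HR 1.00. The statistic equals the landmark statistic exactly, because the risk set at each later event time is the same under either clock.

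**4. Log-rank, post-progression samples included.** Assumptions not in the documents: the marker is high in 80% of those already progressed and 40% of the rest, with no effect on later hazard; a share of early progressors is still sampled at Cycle 4 Day 1. With median 4 months and 6-week scans:

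| Early progressors sampled | Rejection, nominal 10% | Rejection, nominal 5% |
|---|---|---|
| 10% | 10% | 5% |
| 25% | 17% | 10% |
| 50% | 28% | 20% |

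Repeat runs differ by two or three points. The landmark test on the same data stays near 10% at the nominal 10% level. The 5% column is the level SAP 4.7.1 sets for non-bTMB tests.

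**5. Low tumor content (secondary, conditional).** Suppose, as an assumption, that ORR is 20% and follow-up samples below 1% MSAF were dropped. If 80% of responders and 20% of non-responders fell below 1%, ORR among retained patients would be 0.2×0.2/(0.2×0.2 + 0.8×0.8) = 0.04/0.68 = 5.9%. Crossing losses of 50-90% in responders with 10-30% in non-responders gives 2.7% (0.02/0.74) to 15.2% (0.10/0.66).

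**The case against.** The strongest reply is that 4.7.3 is brief and permissive. It says summarized, and Protocol 6.6.3 says only that status may be examined. The PBMC analysis is optional and could use the pre-dose Cycle 1 sample. Change in bTMB is not tied to PFS. The stated purpose of the progression draw is to compare radiographic findings with bTMB change and to explore resistance. All of this stands, and it limits the point to how the cross-reference would be carried out. It does not remove the point: the only method referenced is the baseline one, applied to markers at timepoints that include on-treatment draws.

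Three stronger readings are tempting and are not supported.

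- A reader might infer that every log-rank p-value from these analyses is inflated. Step 3 shows otherwise; inflation needs a further step, such as using post-progression samples. Larger figures arise if unsampled patients are counted as unfavourable (95% rejection at nominal 10%) or timepoints are pooled as ever favourable (70%), but the SAP describes neither.
- A reader might infer that follow-up samples are filtered at 1% MSAF, so that bTMB change is measured mainly in non-responders. The SAP states that condition only for the population defined by the baseline sample, and it concerns the bTMB assay, not PBMC or other markers.
- A reader might infer that the progression sample will be split high versus low against PFS. No passage says so; the SAP merely does not exclude it.

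The analyses are also exploratory, in a study the protocol describes as hypothesis-generating.

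**Conclusion.** The point holds in limited form. Followed as written, 4.7.3 overstates Kaplan-Meier medians and PFS rates by on-treatment marker: about 6.1 against 4.0 months at Cycle 4 Day 1 if median PFS is 4 months. This needs no assumption about the marker. The log-rank comparison is sound for event-free patients sampled at one timepoint. It can exceed its level if post-progression samples enter, by an amount that depends wholly on the assumed marker shift and share sampled: from no inflation at 10% sampled to 28% (nominal 10%) or 20% (nominal 5%) at 50% sampled. The MSAF point is an inference about an unstated rule, so it is a request for clarification. The primary ORR analysis, the gatekept bTMB tests at 16 and 10, and the power table are unaffected.

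**What to change.** In SAP 4.7.3:

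1. For each on-treatment sample (Cycle 2 Day 1, optional Cycle 3 Day 1, Cycle 4 Day 1), specify a landmark analysis. Include only patients event-free and sampled at that day, and count PFS and OS from it.
2. Use the progression sample for resistance and change analyses only, not for PFS comparisons.
3. For change in bTMB, report follow-up samples below 1% MSAF as their own category, with counts by best response, so that they are not silently dropped.

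The cost is SAP wording and programming; no new samples are needed. Patients with early events, about 20-30% by Cycle 4, leave these exploratory comparisons. At the 30% end, 150 patients become about 105.
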